participant's current pain condition (presence of sciatica), potential prognostic risk for pain-related impairment (e.g., pain catastrophizing, fear avoidance, treatment expectations, and disability/workers compensation), and pain-related service use (e.g., back surgery, injections, opioid and other common prescription medications, various types of exercise, psychological counseling, and use of acupuncture) align with RTF recommendations or are specific to the study's focus on acupuncture. We will measure patient expectations of acupuncture using one item from the EXPECT short form⁶² and using the term acupuncture as the therapy. The question uses a 0 to 10 scale focused on expectations related to acupuncture treatment for chronic low back pain. We will include questions about the impact of the COVID-19 pandemic on the ability to get health care and on their overall health (physical, emotional, and mental, including pain). These were adapted from a patient questionnaire developed by the Pain Management Collaboratory funded by the NIH – Department of Defense and Veterans Administration⁶³. We will ask several questions from the FRAIL scale to characterize participant frailty at the time of enrollment in this study. Finally, we will also collect data from the EHR on other co-morbidities, including various pain conditions. This will allow us to describe the population as well as conduct some moderator analyses.

Aim 1 measures (Baseline AND 3, 6 and 12-monthfollow-up).

Back-related disability will be measured with the 24-item Roland-Morris Disability Questionnaire (RMDQ),⁶⁴ which asked whether 24 specific activities were limited due to back pain during the past week (yes or no). This legacy measure has been found to be reliable, valid and sensitive to clinical changes.⁶⁵⁻⁶⁹ It is appropriate for telephone administration for patients with moderate disability.⁷⁰ The RMDQ will be our primary outcome measure and will be measured as a continuous variable. The minimal clinically important difference (MCID) for the RMDQ in our population is 2 points⁷¹ or 30% improvement from baseline.⁷² The MCID will be examined in a secondary analysis.

As a secondary outcome measure and a HEAL CDE, we will use the PEG scale (a validated, 3-item pain-intensity and pain-related interference composite measure assessing Pain intensity, as well as pain interference with Enjoyment of Life and General Activity).⁷⁵

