### 3. Additional Variables for Effectiveness Analyses (Moderators and Predictors)

The following predictors/covariates and/or **moderators** will be assessed related to the **primary outcome**. Note: variables pre-specified for baseline adjustment in all models include: baseline outcome value, age, sex, race, and healthcare system

Moderators & Predictors	Definition	Role	Data Source
Sex	Male vs. Female/Other Sex at birth as reported by subject; assessed using HEAL CDE Demographic question	Moderator/Predictor	Patient self-report at baseline
Age	65-74, 75-84, 85+	Moderator/Predictor	EHR
Race/Ethnicity	White, non-white	Moderator/Predictor	Patient self-report at baseline
Expectations of acupuncture	EXPECT 1-item question – categorical based on the distribution of responses	Moderator/Predictor	Patient self-report at baseline
RMDQ	<18, 18+	Moderator/Predictor	Patient self-report at baseline
Pain catastrophizing	6-item subscale required by HEAL CDE	Predictor/covariate	Patient self-report at baseline

Moderators & Predictors	Definition	Role	Data Source
Fear avoidance	NIH Task Force single item	Predictor/covariate	Patient self-report at baseline
Frailty	Frailty Index 	Predictor/covariate	Patient self-report at baseline and EHR data
Medical morbidity	Carey Ambulatory-based Morbidity Score 	Predictor/covariate	EHR data; based on last 12 months
Multiple non-malignant musculoskeletal pain conditions	1 pain cluster vs. >1 > 1 pain-related ICD-10 diagnosis corresponding to more than one (>1) of the non-malignant musculoskeletal chronic pain condition clusters developed for the National Pain Strategy chronic pain condition clusters  Back pain Neck pain Limb/extremity pain, joint pain and arthritic disorders Fibromyalgia Headache Orofacial, ear, and temporomandibular disorder pain Musculoskeletal chest pain General pain subcategory of the Other painful conditions cluster	Predictor/covariate	EHR data; diagnoses in participant's EHR extracted at baseline for prior 360 days
Mental health mood disorders	ICD-10 diagnosis for depression and/or anxiety diagnosis	Predictor/Covariate	EHR data; diagnoses in subject's EHR extracted at baseline for prior 360 days

Moderators & Predictors	Definition	Role	Data Source
COVID19 pandemic impact	Two questions modified from assessments designed by Pain Collaboratory. These focus on impacts of ability to get health care and on overall health	Time-varying covariate	Patient self-report

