#### 4. Sample Size and Treatment Assignment Procedures

We determined our sample size requirements for our primary outcome the RMDQ at 6-months that focuses on detecting differences of each acupuncture group compared to UMC. Recruited older adults with cLBP will be randomized, in equal proportions, to one of the three groups (UMC, SA, and EA). The power calculation below was conducted under assumptions of a 20% loss-to-follow-up rate and a SD of 6 points in RMDQ score in each arm (consistent or larger than results from previous trials), and that pairwise comparisons will only be conducted if the omnibus F-test is statistically significant at a 0.05 level to control for multiple comparisons (Fisher's Least Significance Difference multi-comparison approach). Given a sample of 789 total participants (263 per arm) among whom 630 (210 per arm) complete their 6-month follow-up data collection, we will have at least 90% power to detect a MCID of 2 points on the RMDQ score between each acupuncture group and UMC (pair-wise comparison power). Nevertheless, in the scenario where SA at 6-months attenuates to be equivalent to UMC and EA has a 2-point MCID improvement relative to both SA and UMC, we will have 91% power to detect a difference between SA and EA as well as between UMC and EA (each pair-wise comparison).

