## **8. Multiple Comparisons**

We have one primary outcome – the change on RMDQ scores for low-back pain related disability at 6 months since baseline. To control for multiple comparisons due to 3 intervention groups we will apply Fisher's Least Significant Difference approach in which first an omnibus Wald-test for any statistically significant difference

between the three groups is evaluated at the 0.05 alpha level. If the omnibus test is statistically significant, then the pair-wise differences are then evaluated, each using two-sided alpha=0.05. If the omnibus test is not statistically significant, we will conclude that there is no benefit of acupuncture for that time point. In addition, secondary analyses will use a similar approach as that described for the primary outcome to control for the three group comparisons.

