## 9. Missing Data

The investigators and data managers will monitor data collection process on a weekly basis and ensure a minimal amount of loss to follow-up in the study. All analyses will be conducted following an intent-to-treat approach, including all individuals randomized regardless of their engagement with, or exposure, to the intervention. If missing data for RMDQ is minimal, our primary analysis will be a complete case analysis adjusting for baseline RMDQ score, age, sex, race and HCS. If missing data for RMDQ at 6 months is above 15% in any arm, or differential by 10% between any two arms, then for our primary analysis we will employ missing not at random imputation techniques to address missing data issues. Though the metric used to make decisions about the analysis method focuses on missing data at the primary time point (6 months), if criteria are met missing data will be imputed 3, 6 and 12-month time points. However, our focus will be on minimizing missing data, and in our collective substantial experience conducting similar trials, we have consistently had retention in line with this. Should it be necessary, the imputation method we propose, derived for use with GEE and sensitive to potential non-ignorable missingness, includes all follow up time points in the same model and uses a pattern mixture approach that relaxes the missing at random given baseline covariates assumption. This accomplished via the implementation of an imputation model which includes indicators classifying the mutually exclusive missing data patterns observed across all time points in the data. We will describe all of the missing data patterns present in the observed data to identify a scientifically reasonable and estimable set of patterns to use as indicators in imputation models for each outcome. Specifically, following the recommendations of Wang and Fitzmaurice, we plan to use the most flexible (parameterizing the largest number of missing patterns) that are estimable with the data. We will construct the imputation models such that the effects of missing data on the outcome are allowed to vary by treatment arm and follow-up time and will include main effects for all covariates used as stratification factors in the study randomization and/or thought to be potential confounders of the relationship between outcome and treatment arm. Further, we will include additional baseline variables that are predictive of missing the 6 months outcome. Specifically, baseline covariates that are significantly (at 0.10 significance level) associated with missingness at 6 months using flexible logistic regression models will be included as main effects in imputation models.

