## 13. Effectiveness Analyses on Changes in RMDQ Scores

We will evaluate the effectiveness of acupuncture and acupuncture plus maintenance relative to Usual Medical Care (UMC) at 3-, 6- (primary time-point), and 12-months after randomization. We will conduct a longitudinal analysis including the continuous outcome, change in Roland Morris Disability Questionnaire (RMDQ) from baseline (primary outcome) measured at all follow-up times, in one model estimated using generalized estimating equations (GEE).  We will use a working independence correlation matrix and will calculate standard errors using the robust sandwich estimator to account for within-person and within-in provider (some participants may see the same provider) correlation. All models will adjust for baseline RMDQ score, age, sex, race and HCS. Further, if missing RMDQ at 6 months (primary time point) is more than 15% in any study arm, or differential by more than 10% between any two arms, we will use imputation approaches as the primary analysis to account for missing data and further adjust for any baseline variables that are predictive of loss to follow-up determined as described in Section 9. All analyses will be conducted following an intent-to-treat approach, including all individuals randomized regardless of their engagement with, or exposure, to the intervention.

We will include interactions between intervention groups and time (3-, 6-, and 12-months) to estimate time-specific intervention effects. Time will be included as a categorical variable. To gain power, since acupuncture and acupuncture plus maintenance at 3-months are the same intervention (maintenance period occurs between 3 and 6 months post randomization and neither participants in the EA condition nor the acupuncturists treating them will be aware they will receive maintenance treatments until close to the 3-month follow-up), we will combine acupuncture groups at 3-month follow-up. We chose GEE as our analytic method because our primary outcome, RMDQ, is not expected to be normally distributed. From our experience working with RMDQ data, adjusting for baseline RMDQ value results in more normally distributed residuals. However, we didn't want to make that assumption a priori and therefore chose GEE.

Our specific model for change in RMDQ is the following:

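### The primary RMDQ model leaves out baseline factors that the protocol calls prognostic and the SAP labels predictors: a modest loss of precision and an adjustment set that is not fully fixed

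*Protocol*

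**What the plan says.** Protocol 6.2.2 (Baseline Interview) describes items on "potential prognostic risk for pain-related impairment (e.g., pain catastrophizing, fear avoidance, treatment expectations" among the questions asked before randomisation. SAP section 3 tabulates variables to be assessed in relation to the primary outcome. It gives pain catastrophizing and fear avoidance the role of predictor/covariate and acupuncture expectation the role of moderator/predictor. Frailty, medical morbidity, multiple pain conditions and mood disorder diagnosis are also listed as predictor/covariate.

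The same section limits adjustment: "variables pre-specified for baseline adjustment in all models include: baseline outcome value, age, sex, race, and healthcare system". SAP section 13 repeats this for the primary models: "All models will adjust for baseline RMDQ score, age, sex, race and HCS".

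Further variables come in through SAP sections 9 and 13, and only if 6-month RMDQ is missing for more than 15% in any arm or missingness differs between two arms by more than 10%. Those added are baseline variables "significantly (at 0.10 significance level) associated with missingness at 6 months". When imputation is used, section 9 also puts potential confounders in the covariate vector Z without listing them.

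Protocol 9.6 differs. It adjusts all models for baseline outcome, age, sex and HCS, without race, and adds predictors of loss to follow-up with no trigger stated for that step.

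**The concern.** The plan identifies factors expected to predict the outcome, measures them in every arm before randomisation, labels them predictors, and then places none of them in models (1) and (2). The one explicit selection test looks for association with missingness. A variable can be strongly prognostic for RMDQ and unrelated to dropout, or the reverse, so that test is not a route to precision.

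Two things are at stake. The first is the width of the intervals for EA–UMC, SA–UMC and EA–SA. It matters most for EA–SA, because that test decides in SAP 13.1 whether the acupuncture arms are pooled. The second is how firmly the covariate set is fixed. A predictor/covariate label attached to no primary model, an undefined class of potential confounders, and a protocol rule that differs from the SAP leave part of the set to later judgement.

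**Working it through.** **Inputs.** From SAP sections 4, 7 and 8: 1:1:1 allocation; 263 randomised and 210 analysed per arm; "a SD of 6 points in RMDQ score in each arm"; an omnibus test at 0.05, then pairwise tests "each using two-sided alpha=0.05". SAP section 4 also reports, from an earlier trial, SDs of 5.42 for the 6-month score and 5.11 for the change score.

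**Stated power.** The SAP says "we will have at least 90% power to detect a MCID of 2 points on the RMDQ score" and, if only EA works, "we will have 91% power to detect a difference between SA and EA as well as between UMC and EA".
- SE of a difference = 6 × √(2/210) = 0.586. The 95% half-width is 1.96 × 0.586 = 1.148, against 1.15 stated.
- Ungated pairwise power = Φ(2/0.586 − 1.96) = 92.7%.
- With the omnibus gate, by simulation: 91.2% for each arm against UMC when both gain 2 points, and about 91% for both contrasts when only EA gains 2.
- 210/0.80 = 262.5, so 263 per arm.

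The stated figures reproduce, and they take no credit for covariates. The omission therefore does not break them.

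**Which branch is likely.** Planned loss is 1 − 210/263 = 20.2%, above the 15% trigger. If that loss occurs, the imputation branch is the primary analysis, and the undefined potential confounders become relevant.

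**Gain from adjustment.** Let R² be the share of residual variance explained beyond baseline RMDQ, age, sex, race and HCS. The documents give no value; I assume 2–8%.
- SE factor = √(1 − R²): √0.98 = 0.990 and √0.92 = 0.959, so the SE falls by 1.0–4.1%.
- Equivalent completers = 630/(1 − R²) − 630: 12.9 at 2% and 54.8 at 8%.
- Half-width at SD 6: 1.148 × 0.990 = 1.136 and 1.148 × 0.959 = 1.101.

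Power was simulated with three arm means, 210 per arm and SD × √(1 − R²), using the omnibus Wald test (2 df, 0.05) and then pairwise tests at 0.05. F and t references instead of chi-square and normal lower the EA–UMC figures by about 0.1 to 0.3 percentage points.

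| Contrast and true gains over UMC | SD | No added terms | R² 2–8% |
|---|---|---|---|
| EA–UMC; SA 1, EA 2 | 6 | 86.9% | 87.5–89.8% |
| EA–UMC; SA 1, EA 2 | 5.11 | 95.6% | 96.0–97.0% |
| EA–SA; SA 1, EA 2 | 6 | about 40% | 40–43% |
| EA–SA; SA 1, EA 2 | 5.11 | about 52% | 53–55% |
| Each arm–UMC; both 2 | 6 | 91% | 92–93% |
| Each arm–UMC; both 2 | 5.11 | 97.6% | 97.8–98.4% |

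The EA–SA rows ignore the further condition in SAP 13.1 that the difference exceed 1 point. As an outer bound, R² of 20% would cut the SE by 10.6%; nothing in the documents supports a value that high.

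**Which SD applies.** R² here is measured after adjustment for baseline RMDQ, whereas SD 6 is for the unadjusted score and was set high on purpose to cover clustering and multi-site variability. If the baseline SD equals the 6-month SD of 5.42 (an assumption), the correlation is 1 − 5.11²/(2 × 5.42²) = 0.56 and the adjusted SD is 5.42 × √(1 − 0.56²) ≈ 4.5. Ungated power for 2 points is then about 99.5% before any further covariate. Without clustering, the SD 5.11 rows are the more realistic ones.

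**The case against.** The strongest defence is that the primary model already adjusts for the baseline outcome, usually the most important covariate, and for every stratification factor. The set is stated twice in the SAP, and SAP section 7 assigns the primary analysis to a fully blinded biostatistician. On that view a longer list is preference. Much of this stands. The default model is sound and prespecified, the EA–UMC and SA–UMC contrasts gain little at SD 5.11, and EA–SA at 1 point remains underpowered with or without the added terms. The protocol itself does not expect a clinically important EA–SA difference.

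Several stronger readings are tempting, and the documents do not support them:
- *That these factors enter no outcome model.* Expectation is one of five prespecified moderators of 6-month RMDQ change. Frailty, co-morbid pain and depression may be moderators if a subgroup exceeds 10% (SAP 15.1). The dose and adherence models add confounders (SAP 15.2).
- *That predicting missingness is the only way in.* SAP section 9 also admits potential confounders once imputation is used.
- *That the precision is free.* A missing-baseline rule and a sensitivity model are needed.
- *That chance imbalance in these factors biases the comparison.* Under randomisation it does not; adjustment is a matter of precision.
- *That the trial is underpowered for its stated target.* The stated power reproduces.

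The defence leaves one gap unanswered: variables labelled predictors of the primary outcome have no prespecified place in its primary model, and the class of potential confounders is undefined.

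**Conclusion.** The point holds as one of efficiency and clarity. Pain catastrophizing, fear avoidance and acupuncture expectation are treated as prognostic but are not prespecified in models (1) and (2), and the SAP's conditional routes into the primary analysis do not select on prognosis for RMDQ. The likely cost is a standard error 1–4% larger than necessary. For EA–UMC with gains of 1 and 2 points, that is worth up to about 3 percentage points of power at SD 6 and under 1.5 at SD 5.11. For EA–SA at 1 point it is worth up to about 3 points at either SD.

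These sizes rest on an assumed partial R² of 2–8%, 210 completers per arm and no clustering. If the factors add nothing beyond baseline RMDQ, there is no gain. The need to settle the covariate set and reconcile the two documents does not depend on that assumption.

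**What to change.** Before unblinding:
- Name in SAP section 13 a short fixed set of self-reported baseline terms to add to Z in models (1) and (2) and to the imputation model: pain catastrophizing, fear avoidance and acupuncture expectation. Baseline PEG and PROMIS physical function are optional additions suggested here; the protocol passage on prognostic risk does not name them.
- State the form of each term. SAP section 3 makes expectation categorical, so a linear 0–10 term for adjustment should be declared separately from the moderator analysis.
- Fill missing baseline values with the overall mean, so that nobody is dropped.
- Keep the five-covariate model as a sensitivity analysis.
- Relabel the SAP section 3 variables that enter no primary model. The COVID-19 item is time-varying and does not belong in the baseline set.
- List the potential confounders in SAP section 9 or delete the term.
- Reconcile Protocol 9.6 with SAP sections 9 and 13 on race and on when predictors of loss to follow-up enter.

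The measures are already collected, and three to five more terms on about 630 completers cost negligible degrees of freedom. With a linear mean model and robust standard errors, the treatment contrast still targets the same mean difference. The price is a longer model description, a missing-baseline rule and one extra sensitivity model.
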